2. INTRODUCTION

Single 2 gram (g) and single 4 g doses of zoliflodacin were safe and well-tolerated in previous clinical trials. The 2 g dose has been selected as the therapeutic dose for further clinical testing of zoliflodacin. The 4 g dose was shown to result in drug exposures higher than the 2 g dose and should provide exposures that will be achieved in patients when used with other drugs that may interact with zoliflodacin. For this reason, the 4 g dose was selected as the suprathreshold dose for this TQT trial. Placebo for zoliflodacin was selected to control for natural diurnal changes in the electrocardiogram (ECG). Moxifloxacin was selected as a positive comparator to evaluate assay sensitivity for QT interval of the ECG corrected using Fridericia's formula (QTcF), as it predictably causes a mild prolongation of the QTcF interval but has a very low risk for inducing cardiac arrhythmias.

2.1. Purpose of the Analyses

The main text of this SAP discusses analysis of safety and pharmacokinetic (PK) endpoints for the study. Analyses of Holter ECG endpoints (including changes in QTcF and other ECG intervals, T-wave morphology and other ECG effects), as well as drug concentration-QTcF modeling are presented in the ECG SAP ([Appendix 4](#)).

3. STUDY OBJECTIVES AND ENDPOINTS

3.1. Study Objectives

Primary:

- To evaluate the effect of zoliflodacin on the QTcF interval

Secondary:

- To evaluate the effects of zoliflodacin on other ECG parameters (PR, QRS, and RR intervals, and heart rate)
- To evaluate the sensitivity of QTcF measurement using moxifloxacin
- To evaluate the effect of zoliflodacin on T-wave morphology
- To evaluate the PK of 2 g and 4 g oral zoliflodacin under fasting state
- To evaluate the relationship between zoliflodacin PK and time-matched QTcF pharmacodynamics (PD)
- To evaluate the safety and tolerability of 2 g and 4 g oral zoliflodacin

3.2. Endpoints

Primary:

- The upper bound of the one-sided 95% confidence interval (CI) for the largest time-matched, placebo-corrected, baseline-adjusted mean QTcF interval ($\Delta\Delta\text{QTcF}$) collected in the 24 hour (h) period after 2 g and 4 g dose of zoliflodacin is <10 milliseconds (msec)

Secondary:

- Time-matched, placebo-corrected, baseline-adjusted non-QT intervals (PR, QRS and RR intervals) and heart rate collected in the 24 h period after 2 g and 4 g dose of zoliflodacin
- The lower bound of the one-sided 95% CI of the $\Delta\Delta\text{QTcF}$ is >5 msec at one or more individual timepoints between 1 h and 4 h after a single dose of moxifloxacin 400 milligrams (mg)
- Incidence of abnormal T-wave morphology using defined categories in the 24 h period after 2 g and 4 g dose of zoliflodacin
- Single-dose plasma concentrations (and PK exposure parameters, such as maximum concentration [C_{\max}] and area under the curve [AUC]) of zoliflodacin collected up to 24 h after 2 g and 4 g dose of zoliflodacin
- Relationship between plasma concentrations of zoliflodacin (and PK and exposure parameters, such as C_{\max} and AUC) and $\Delta\Delta\text{QTcF}$ up to 24 h after 2 g and 4 g dose of zoliflodacin
- Occurrence of treatment-emergent serious adverse events (SAEs), other unsolicited treatment-emergent adverse event (AEs), and changes from baseline in vital signs, clinical laboratory values, and ECG parameters following administration of zoliflodacin and moxifloxacin from time of dosing to Final Visit, or early termination (ET) Visit

3.3. Study Definitions and Derived Variables

Dosing Periods

Dosing period may be described numerically (1, 2, 3, or 4) or in terms of the treatment received during the period (2 g zoliflodacin, 4 g zoliflodacin, placebo, or 400 mg moxifloxacin). Analysis of safety endpoints will be performed by treatment received for the period, not by the period number.

Period 1: From start of first Check-in day (Day -1) through the day before Check-in for the second dose, or ET Visit, whichever occurs first.

Period 2: From start of second Check-in day through the day before Check-in for the third dose, or ET Visit, whichever occurs first.

Period 3: From start of third Check-in day through the day before Check-in for the fourth dose, or ET Visit, whichever occurs first.

Period 4: From start of fourth Check-in day through Final Visit, or ET Visit, whichever occurs first.

Baseline

Baseline is defined for safety analyses as follows.

- Measurements prior to the first dose will not have a baseline defined.
- Measurements after the first dose, and prior to the second dose (including Period 2 check-in and pre-dose measurements and early termination measurements after the first dose and prior to the second dose) will use the last measurement prior to the first dose as baseline.
- Measurements after the second dose, and prior to the third dose (including Period 3 check-in and pre-dose measurements and early termination measurements after the second dose and prior to the third dose) will use the last measurement prior to the second dose as baseline.
- Measurements after the third dose, and prior to the fourth dose (including Period 4 check-in and pre-dose measurements and early termination measurements after the third dose and prior to the fourth dose) will use the last measurement prior to the third dose as baseline.
- Measurements after the fourth dose will use the last measurement prior to the fourth dose as baseline.
- Measurements taken during the Final Visit will use the last measurement prior to the first dose as baseline for the analysis time points labeled “Final Visit” and will use the last measurement prior to the fourth dose as baseline for the analysis time points labeled “Follow-up”. Listings will show both of the two change from baseline values for Final Visit. The justification for including the Period 1 baseline for the Final Visit is to show overall changes (ideally absence of changes) over the course of the study. Grading of change from baseline will be based on the Period 1 baseline only.

Treatment Associated with Records

Treatment associated with post-dose records will always be the last type of treatment received before the (start) date or date-time associated with the record. AEs will be summarized by treatment and listings of all safety endpoints will include treatment, as it is defined here.

Possible values of treatment, in order of presentation in the CSR, are: 2 g zoliflodacin, 4 g zoliflodacin, placebo, and 400 mg moxifloxacin.

Study Day and Day in Period

Study Day and Day in Period will primarily be used in listings to refer to timing of assessments and events relative to first dosing (Study Day) or dose for the respective period (Day in Period).

The day that the first dose of study product is received is considered Study Day 1 for each subject. The day prior to first dose is considered Study Day = -1, not Study Day = 0.

The day that the dose of study product is received is considered Day in Period = 1 for each subject and each dosing period. The day prior to dosing for each period is considered Day in Period = -1, not Day in Period = 0.

Treatment Sequence

Each subject will receive one dose orally of each of four treatments, labeled A through D:

- Treatment A: zoliflodacin 2 g
- Treatment B: zoliflodacin 4 g
- Treatment C: placebo
- Treatment D: moxifloxacin 400 mg

Each subject will be randomly allocated to one of 12 dosing sequences before dosing on Day 1, Dosing Period 1, and receive a single dose of the preceding four study drugs on different days according to their randomly-assigned dosing sequences. The 12 dosing sequences, in order that they will be presented in the report, are ABCD, ACDB, ADBC, BADC, BDCA, BCAD, CDAB, CABD, CBDA, DCBA, DBAC, and DACB.

Sequences will be referred to using these labels in TFLs. The four-letter codes for sequence indicate the order that the treatments will be given to the subject. For example, sequence CABD indicates that the subject would receive placebo in period 1, 2 g zoliflodacin in period 2, 4 g zoliflodacin in period 3, and 400 mg moxifloxacin in period 4.

Tolerability

Tolerability of zoliflodacin will be defined as follows. Tolerability will be concluded for a subject unless any one of the following occurred after receiving zoliflodacin as the most recent non-placebo dose: 1) subject discontinued study drug due to an AE, 2) subject choose to withdraw from the study due to an AE at any time from first dose of zoliflodacin until end of study, or 3) subject was withdrawn from the study by the investigator due to an adverse event at any time from first dose of zoliflodacin until end of study. Withdrawal or discontinuation of study drug after moxifloxacin as the most recent dose will not lead to a conclusion that zoliflodacin was not tolerable.

Visit and Time Point Names for Analysis of Safety and PK Endpoints

Analyses of clinical laboratory results, vital signs, ECG, and PK will be performed by planned time point, expressed as time in h relative to the most recent dose, within period. Labels for each time point are shown in [Table 1](#), including the order the time points will be shown in TFLs and abbreviated labels. The Max Severity Post-Baseline time point is a derived, conceptual time point used in tables displaying severity grading. All other time points refer to planned assessments per the protocol.

The “Follow-up” analysis time points refer to either Check-In visits for the next period (for analysis of treatments given in Period 1, 2, or 3) or to the Final Visit with Pre-dose 4 as baseline. For each treatment, if the treatment was given in Period 1, Period 2, or Period 3, then the pre-dose vital signs and ECG measurements prior to the next dose will be summarized. Listings will use protocol time point names rather

than analysis time point names, e.g. “Check-in” rather than “Follow-up” and “Pre-dose” rather than “Pre-dose (Prior to Next Dose).”

Table 1: Analysis Time Points for Safety and PK Endpoints

Order	Period	Analysis Time Point	Abbreviated Label	Endpoints	Baseline
1	1	Check-In	Day -1	Clinical Laboratory Results, Vital Signs, ECG	N/A
2	1	Pre-dose	0 h	Vital Signs, ECG, PK	N/A
3	1	Max Severity Post-Baseline	N/A	Clinical Laboratory Results, Vital Signs, and ECG Toxicity Grading	N/A
4	1	0.5 h Post-dose	0.5 h	PK	N/A
5	1	1 h Post-dose	1 h	Vital Signs, ECG, PK	Pre-dose 1
6	1	2 h Post-dose	2 h	Vital Signs, ECG, PK	Pre-dose 1
7	1	3 h Post-dose	3 h	PK	N/A
8	1	4 h Post-dose	4 h	Vital Signs, ECG, PK	Pre-dose 1
9	1	6 h Post-dose	6 h	PK	N/A
10	1	8 h Post-dose	8 h	PK	N/A
11	1	12 h Post-dose	12 h	PK	N/A
12	1	24 h Post-dose	24 h	Clinical Laboratory Results, Vital Signs, ECG, PK	Pre-dose 1
13	2	Follow-up	FU	Clinical Laboratory Results, Vital Signs, ECG	Pre-dose 1
14	2	Pre-dose (Prior to Next Dose)	0 h	Vital Signs, ECG	Pre-dose 1
14	2	Pre-dose	0 h	PK	N/A
15	2	Max Severity Post-Baseline	N/A	Clinical Laboratory Results, Vital Signs, and ECG Toxicity Grading	Pre-dose 2
16	2	0.5 h Post-dose	0.5 h	PK	N/A
17	2	1 h Post-dose	1 h	Vital Signs, ECG, PK	Pre-dose 2
18	2	2 h Post-dose	2 h	Vital Signs, ECG, PK	Pre-dose 2
19	2	3 h Post-dose	3 h	PK	N/A
20	2	4 h Post-dose	4 h	Vital Signs, ECG, PK	Pre-dose 2
21	2	6 h Post-dose	6 h	PK	N/A
22	2	8 h Post-dose	8 h	PK	N/A
23	2	12 h Post-dose	12 h	PK	N/A
24	2	24 h Post-dose	24 h	Clinical Laboratory Results, Vital Signs, ECG, PK	Pre-dose 2
25	3	Follow-up	FU	Clinical Laboratory Results, Vital Signs, ECG	Pre-dose 2
26	3	Pre-dose (Prior to Next Dose)	0 h	Vital Signs, ECG	Pre-dose 2
26	3	Pre-dose	0 h	PK	N/A
27	3	Max Severity Post-Baseline	N/A	Clinical Laboratory Results, Vital Signs, and ECG Toxicity Grading	Pre-dose 3
28	3	0.5 h Post-dose	0.5 h	PK	N/A
29	3	1 h Post-dose	1 h	Vital Signs, ECG, PK	Pre-dose 3

Order	Period	Analysis Time Point	Abbreviated Label	Endpoints	Baseline
30	3	2 h Post-dose	2 h	Vital Signs, ECG, PK	Pre-dose 3
31	3	3 h Post-dose	3 h	PK	N/A
32	3	4 h Post-dose	4 h	Vital Signs, ECG, PK	Pre-dose 3
33	3	6 h Post-dose	6 h	PK	N/A
34	3	8 h Post-dose	8 h	PK	N/A
35	3	12 h Post-dose	12 h	PK	N/A
36	3	24 h Post-dose	24 h	Clinical Laboratory Results, Vital Signs, ECG, PK	Pre-dose 3
37	4	Follow-up	FU	Clinical Laboratory Results, Vital Signs, ECG	Pre-dose 3
38	4	Pre-dose (Prior to Next Dose)	0 h	Vital Signs, ECG	Pre-dose 3
38	4	Pre-dose	0 h	PK	N/A
39	4	Max Severity Post-Baseline	N/A	Clinical Laboratory Results, Vital Signs, and ECG Toxicity Grading	Pre-dose 4
40	4	0.5 h Post-dose	0.5 h	PK	N/A
41	4	1 h Post-dose	1 h	Vital Signs, ECG, PK	Pre-dose 4
42	4	2 h Post-dose	2 h	Vital Signs, ECG, PK	Pre-dose 4
43	4	3 h Post-dose	3 h	PK	N/A
44	4	4 h Post-dose	4 h	Vital Signs, ECG, PK	Pre-dose 4
45	4	6 h Post-dose	6 h	PK	N/A
46	4	8 h Post-dose	8 h	PK	N/A
47	4	12 h Post-dose	12 h	PK	N/A
48	4	24 h Post-dose	24 h	Clinical Laboratory Results, Vital Signs, ECG, PK	Pre-dose 4
49	4	Follow-up	FU	Clinical Laboratory Results, Vital Signs, ECG	Pre-dose 4
50	4	Final Visit	N/A	Clinical Laboratory Results, Vital Signs, ECG	Pre-dose 1

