9. SAFETY EVALUATION

All safety analyses will be presented using the safety population. Subjects will be grouped for summary statistics by Treatment, as defined in Section 3.3.

When calculating the incidence of AEs (i.e., on a per subject basis), each subject will be counted once and any repetitions of unsolicited AEs within a subject (by treatment) will be ignored for events coded in the same category by the Medical Dictionary for Regulatory Activities (MedDRA®). The denominators for percent values will be indicated within the table or table header and denominators will consist of the maximal size of the safety population in the indicated observation period. Moreover, events thus summarized will be coded to the highest severity observed. If the time interval defined by the start date and end date of the AE overlaps more than 1 period, the AE will be associated with treatment immediately preceding the AE start date only, and the AE will be graded according to the maximum severity of the event at any time prior to the AE end date. Abnormal laboratory values or clinical findings measured after dosing will be reported using the toxicity scales in [Table 3](#) and [Table 4](#).

All laboratory, vital signs, and ECG results obtained after the first dose that have programmable criteria described in the toxicity scales will be graded for the CSR according to the programmable criteria, and toxicity grades of mild, moderate, or severe will be indicated for the result in the listings. For criteria involving a change from baseline, the baseline to be used is described in Section 3.3.

If a subject was accepted into the trial with a laboratory, vital signs, or ECG parameter value that overlaps with values used for grading Grade 1 laboratory abnormalities, the result will only be graded (mild or worse) if the post-dose measurement of the parameter is different (worse) than baseline. In other words, a result will be graded as mild, moderate, or severe if and only if it both meets the grading criteria in [Table 3](#) or [Table 4](#) and is worse than baseline by any amount.

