14.3.5 Displays of Laboratory Results

14.3.5.1 Chemistry Results

Table 20: Chemistry Clinical Safety Laboratory Results by Parameter, Maximum Severity, Time Point, and Dosing Period

[Implementation Note: If there is not at least 1 Mild, Moderate, or Severe Event for Any Period, Max Severity Post-Baseline, then only the Any Period, Max Severity Post-Baseline row will be shown for the parameter.]

Dosing Period	Time Point	N	Mild		Moderate		Severe	
			n	%	n	%	n	%
Chemistry - Any Parameter								
Any Period	Max Severity Post-Baseline	x	x	x	x	x	x	x
	24 h Post-dose	x	x	x	x	x	x	x
	Final Visit ^b	x	x	x	x	x	x	x
2 g Zoliflodacin	Max Severity Post-Baseline	x	x	x	x	x	x	x
	24 h Post-dose	x	x	x	x	x	x	x
	Follow-up ^a	x	x	x	x	x	x	x
4 g Zoliflodacin	Max Severity Post-Baseline	x	x	x	x	x	x	x
	24 h Post-dose	x	x	x	x	x	x	x
	Follow-up ^a	x	x	x	x	x	x	x
Placebo	Max Severity Post-Baseline	x	x	x	x	x	x	x
	24 h Post-dose	x	x	x	x	x	x	x
	Follow-up ^a	x	x	x	x	x	x	x
400 mg Moxifloxacin	Max Severity Post-Baseline	x	x	x	x	x	x	x
	24 h Post-dose	x	x	x	x	x	x	x
	Follow-up ^a	x	x	x	x	x	x	x
Chemistry – Sodium, Decrease								
Any Period	Max Severity Post-Baseline	x	x	x	x	x	x	x
	24 h Post-dose	x	x	x	x	x	x	x
	Final Visit ^b	x	x	x	x	x	x	x
2 g Zoliflodacin	Max Severity Post-Baseline	x	x	x	x	x	x	x
	24 h Post-dose	x	x	x	x	x	x	x
	Follow-up ^a	x	x	x	x	x	x	x
4 g Zoliflodacin	Max Severity Post-Baseline	x	x	x	x	x	x	x
	24 h Post-dose	x	x	x	x	x	x	x
	Follow-up ^a	x	x	x	x	x	x	x
Placebo	Max Severity Post-Baseline	x	x	x	x	x	x	x
	24 h Post-dose	x	x	x	x	x	x	x
	Follow-up ^a	x	x	x	x	x	x	x

Dosing Period	Time Point	N	Mild		Moderate		Severe	
			n	%	n	%	n	%
400 mg Moxifloxacin	Max Severity Post-Baseline	x	x	x	x	x	x	x
	24 h Post-dose	x	x	x	x	x	x	x
	Follow-up ^a	x	x	x	x	x	x	x
Chemistry – Sodium, Decrease								
...								

Note: The “Max Severity Post-Baseline” rows indicate the maximum severity experienced by each subject at any time point post baseline within the period, including unscheduled assessments. N=Number of subjects in the Safety Population that had clinical safety labs measured at the respective visit.

^a The “Follow-up” analysis time points refer to either Check-In visits for the next period (for analysis of treatments given in Period 1, 2, or 3) or to the Final Visit with Pre-dose 4 as baseline.

^b The “Final Visit” analysis time point uses the last measurement prior to the first dose as baseline.

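### SAP 3.3 grades the Final Visit against the Period 1 baseline only, while Table 1 and the toxicity tables give Pre-dose 4 for the same visit under the Period 4 treatment

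*SAP*

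**What the plan says.** SAP 3.3 (Baseline) first sets a general rule: "Measurements after the fourth dose will use the last measurement prior to the fourth dose as baseline". It then treats the Final Visit separately. Under the label Final Visit, the baseline is the last value before the first dose. Under the second label, Follow-up, the visit "will use the last measurement prior to the fourth dose as baseline for the analysis time points labeled" that way. The justification given for the Period 1 baseline is to show overall change across the study. The paragraph closes with "Grading of change from baseline will be based on the Period 1 baseline only".

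Other parts of the SAP bear on the same visit:

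- SAP 3.3 (Dosing Periods) defines Period 4 as running "From start of fourth Check-in day through Final Visit, or ET Visit, whichever occurs first".
- SAP 3.3 also has a rule for assigning each result to a drug: "Treatment associated with post-dose records will always be the last type of treatment received before the (start) date or date-time associated with the record". Final Visit records therefore carry the Period 4 treatment.
- SAP Table 1 gives Pre-dose 4 for Period 4 Max Severity Post-Baseline (row 39, a grading endpoint) and for Period 4 Follow-up (row 49). It gives Pre-dose 1 only for Final Visit (row 50).
- Toxicity Tables 20, 25 and 28 show graded Follow-up and Max Severity rows under every treatment. Their footnote says Follow-up refers to the next check-in "or to the Final Visit with Pre-dose 4 as baseline". Tables 22 and 24 repeat Table 20.
- SAP 9: "For criteria involving a change from baseline, the baseline to be used is described in Section 3.3". It also grades a result only if it meets the criterion and "is worse than baseline by any amount".
- Tables 17 and 18 list graded laboratory results beside a Treatment column, with the Final Visit change taken from before the first dose.

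**The concern.** One visit has two stated grading baselines. A programmer who follows the closing sentence of the Baseline paragraph breaches Table 1 and the table footnotes. One who follows those breaches the sentence. The footnotes cannot be read as covering change-from-baseline summaries only, because Tables 20, 25 and 28 display grades.

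Safety and tolerability of the two zoliflodacin doses is a secondary objective, and the SAP analyses safety by the treatment received in the period. If the Period 1 rule is applied to the by-treatment rows, drift since before the first dose can appear as a grade under the last treatment, including placebo. A worsening after the fourth dose can also go ungraded because the subject was already at a similar level before the study. If the matter is left open, the choice is made at programming, possibly with data in view.

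**Working it through.** The plan states no figure on this point, so there is none to reproduce. The check is a comparison of texts, a count, and a few illustrative grades.

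**1. Grading baseline for the Final Visit, by source**

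| Source | Final Visit row | Period 4 Follow-up row | Period 4 Max Severity row |
|---|---|---|---|
| SAP 3.3, grading sentence | Pre-dose 1 | Pre-dose 1 | Pre-dose 1 for the Final Visit component |
| SAP 3.3, general rule and Follow-up clause | Pre-dose 1 | Pre-dose 4 | Pre-dose 4 |
| SAP Table 1, rows 50, 49, 39 | Pre-dose 1 | Pre-dose 4 | Pre-dose 4 |
| Footnotes to Tables 20, 25, 28 | Pre-dose 1 | Pre-dose 4 | not stated |

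The sources agree on the Final Visit row, which sits under Any Period. They disagree on the two by-treatment rows.

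**2. Subjects involved**

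Last treatment in the 12 sequences:
- A (2 g): BDCA, CBDA, DCBA
- B (4 g): ACDB, CDAB, DACB
- C (placebo): ADBC, BADC, DBAC
- D (moxifloxacin): ABCD, BCAD, CABD

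Each treatment is last in 3 sequences. With 6 subjects per sequence, 3 × 6 = 18, and 18/72 = 25%. The other 72 − 18 = 54 contribute a next-period check-in, compared with that treatment's own pre-dose value. On the protocol's day numbering, the Period 1 comparison spans about 32 − 1 = 31 days and all four doses.

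**3. Can the grade differ?** Hypothetical values, graded with SAP Tables 3 and 4 and the worse-than-baseline condition:

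| Parameter | Pre-dose 1 | Pre-dose 4 | Final Visit | Grade vs Pre-dose 1 | Grade vs Pre-dose 4 |
|---|---|---|---|---|---|
| QTcF, msec | 395 | 415 | 426 | +31: Grade 2 | +11: none |
| QTcF, msec | 430 | 405 | 440 | +10: none | +35: Grade 2 |
| ALT, male, U/L | 40 | 70 | 60 | worse, 53–115: Grade 1 | not worse: none |

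QTcF Grade 2 includes a rise of 30–59 msec. The choice of baseline can add a grade or remove one.

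**4. Which parameters?** QTcF is the only criterion in SAP Tables 3 and 4 that uses a change from baseline. Bradycardia bands depend on the baseline level. A rate of 51–54 bpm is Grade 1 under the ordinary band but ungraded if baseline was below 60, where Grade 1 is 45–50. The remaining laboratory, vital-sign and PR criteria use absolute limits, so baseline enters only through the worse-than-baseline condition, as in the ALT example.

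**5. Max Severity.** For vital signs and ECG this row also takes in the 1, 2, 4 and 24 h results; for laboratory tests it takes in the 24 h result. In Period 4 all of these use Pre-dose 4. Only the Final Visit component is in dispute.

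**The case against.** The strongest reply is that most of the SAP already points to Pre-dose 4 for the by-treatment rows: the general rule, the Follow-up clause, Table 1 rows 39 and 49, and three table footnotes. On that view the closing sentence has a narrower job. Listings 9, 10, 15 and 17 show two changes at the Final Visit but have room for one severity, so some rule is needed for that single grade. The footnote to Tables 17 and 18 follows the same convention. This reading is plausible, but the SAP does not state it. The sentence carries no such limit, and SAP 9 sends the grading baseline back to 3.3.

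Several further points stand and limit the concern:

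- A reader might infer that the SAP does misattribute grades to the last treatment. It does so only if the 3.3 sentence prevails; if the footnotes are followed, there is no misattribution.
- A reader might infer that 25% of Max Severity entries use the wrong baseline. That does not follow: an entry changes only if the Final Visit decides the maximum, and that share cannot be known from the documents.
- A reader might infer that all safety domains are equally exposed. For most parameters the effect is indirect. Eligibility limits also usually keep entry values out of Grade 1 (male ALT is accepted up to 52 and Grade 1 starts at 53), so the Period 1 baseline will seldom hide a laboratory grade. Some analytes, such as BUN and albumin, do overlap.
- Persisting drug effect is a weak explanation for differences between the baselines, given a half-life of about 6 h and a washout of at least 8 days. Ordinary drift is more likely.

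**Conclusion.** The contradiction is real and should be resolved before the safety tables are programmed. If the 3.3 sentence governs, up to 18 of 72 planned subjects (25%) in each treatment's graded Follow-up row are compared with a value from before all four doses, and the rest with that treatment's own pre-dose value. This count assumes full enrolment and no withdrawals. The plan tolerates up to 16 before replacement, so the number will probably be lower. Max Severity is exposed only through the Final Visit result.

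The direct effect is on standard-ECG QTcF and bradycardia grades. The graded examples are hypothetical and show that the result can move in either direction, not how often it will. A reader might take the QTcF examples to bear on the primary endpoint. They do not: that analysis uses Holter data with its own within-period baseline under the ECG SAP. The point concerns secondary safety displays.

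**What to change.** Replace the closing grading sentence in SAP 3.3 with two statements:

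1. Grading against the Period 1 baseline applies only to the Final Visit row, shown under Any Period.
2. For the Follow-up and Max Severity Post-Baseline rows of the Period 4 treatment, Final Visit results are graded against Pre-dose 4.

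This agrees with Table 1 and with the footnotes to Tables 20, 25 and 28, so those need no change. The Final Visit row still serves the SAP's stated purpose of showing change over the whole study.

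Then align the displays that print a grade beside the Period 4 treatment: Tables 17–19 and Listings 9–11, 15 and 17. Each should either state which baseline the Final Visit grade uses or show both grades. Listings 9, 10, 15 and 17 already carry both changes. The urinalysis displays (Table 19 and Listing 11) have no change column, so there a note or a second grade is needed.

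The cost is a short SAP edit and one extra derived grade at a single visit. No additional data are needed.
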